### **Randomization:**

We will randomize 40 participants 1:1 to the Meals 4 Moms (M4M) and Usual Care (UC) conditions in randomly permuted blocks of size 4 and 6. Randomization will be stratified by site (UCHC vs SFH vs HH) and whether there are children currently living in the participant's home (0 children vs 1+ children) to balance any differences in clinical care and experiences changing diet due to family configuration, respectively. Randomization will be conducted via the randomization module in REDCap based on randomization tables created by [name]. A participant will only be randomized once they have completed all baseline assessments. Study participants will be informed which treatment condition they have been assigned to by a member of the research team.

### **Usual Care:**

Usual care will consist of the current treatment care that is provided by the participant's prenatal care provider. Usual care consists of a special diet, monitoring of blood glucose levels and encouragement/guidance of increasing a participant's exercise.

### **Meals 4 Moms:**

The Meals 4 Moms Program has been developed based on providing continued education and support with a focus on physical activity/fitness and nutrition.

The program is centered around providing a subsidized food prescription program designed to promote the consumption of nutritious GDM-specific meals. My Local Chefs (MLC), a local Connecticut-based small business, that will package and deliver nutrient-rich American Diabetes Association (ADA)-compliant weekly customizable prepared meals that contain locally sourced, culturally acceptable, nutritionally adequate foods and nutritionist-approved GDM-specific recipes that guide participants to make healthy meals at home.

Participants randomized to the M4M condition will receive an individualized URL link to the My Local Chefs website, where they will have access to a meal budget of \$266 food credits per week. Participants will have the ability to customize their selection of meals and produce using this weekly food budget. Prepared meals will be delivered to the participant's home from their first order post-randomization until 1 week after the

participant delivers (on average, 8-11 weeks). Prepared meals will include the recipes, tips for meal preparation and education on nutrients that are being provided.

Additionally, the program will provide participants access to an online platform hosted by My Local Chefs where participants can access enhanced educational GDM-specific education on exercise, nutrition, and blood sugar glucose management. Bite size education will be delivered in a variety of different avenues including videos, podcasts, blog posts and other educational materials.

- Exercise education on the platform will include access to exercise videos that have been reviewed for safety by the study PI. Participants will initially meet virtually or over the phone with the study's exercise trainer to discuss their baseline exercise level and health status to recommend personalized fitness goals during pregnancy. The exercise trainer will make recommendations to which videos will be appropriate for the participant. Participation in the exercise videos will be unsupervised and based on each participants' baseline fitness level (e.g., Tier I [none to minimal daily exercise] and Tier II [moderate exercise]). Participants will then meet with the exercise trainer to review their progress of incorporating exercise into their daily routine on a biweekly basis.

Participants will be instructed to use Move Your Way® from the Office of Disease Prevention and Health Promotion, a free on-line customizable weekly physical activity planner to set exercise goals and track progress. Intervention participants will be provided with an activity tracker to monitor their daily physical activity and Wi-Fi scale to monitor gestational weight gain.

- Nutrition educational resources on the Meals 4 Moms platform will provide participants access to cooking demonstrations, nutritious recipes, featured meals of the week, podcasts and blog posts. Participants who access the platform will not be able to interact in a forum but can comment on blogposts and rate recipes.

#### Activity tracker and digital scale data:

Participants randomized to the M4M condition will be provided with and asked to wear a wearable activity tracker (e.g., a FitBit Inspire 2 or similar model) for the duration of their participation. Subjects randomized to the M4M condition will also be asked to weigh themselves daily using a Wi-Fi scale (e.g., Fitbit Aria Air Scale). Participants will be mailed their hardware within 2-3 days of randomization by study staff. The wearable activity

tracker and Wi-Fi scale will include instructions that detail how to download and use the activity tracker app, how to set up the activity tracker device, and how to wear and charge the device during the study. The instructions are included as an appendix. Study staff will offer additional support over the phone or via videoconference to set up the device and app if needed.

Participants will be asked to weigh themselves daily using the Wi-Fi scale. Activity trackers and scales will be either provided to the participant at a prenatal care visit or shipped to the participant's home address.

The activity tracker app will allow the activity tracker to automatically sync and download data into a secure database (Fitabase). Fitabase is a fully hosted, cloud-based software solution that implements robust industry standards to maintain secure databases and keep data private. M4M participants will be informed that their activity data will be downloaded to the Fitabase. No GPS or other location information is collected.

We expect that M4M participants will spend up to 5 minutes each day unplugging/plugging in their device from the charger and/or keeping track of dates and times when the activity tracker is not worn utilizing a provided tracking log. Participants are expected to wear the activity tracker device as often as possible (20-24 hours per day).

Every two weeks, the exercise trainer will access the Fitabase database to review the downloaded data for each participant.

- The exercise trainer will assess whether M4M participants are meeting the ACOG (American College of Obstetrics & Gynecology) guidelines for exercise in pregnancy. Current recommendations include at least 150 minutes a week/30 minutes exercise 5 times a week. The exercise trainer will suggest to the participant to utilize the additional, PI-approved exercise resources within the curated exercise video library to help increase the level of activity.
- The exercise trainer will also monitor the participant's weights obtained from the Wi-Fi scale. If a participant were to experience a 1.0 kg (2.2lbs) weight gain or any decrease in weight within a week, the exercise trainer will inform the study coordinator and/or PI who will contact the participant's prenatal care provider for appropriate follow-up and management.

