### Subject Characteristics:

#### **Phase 2:**

Age: between 18-49 years old

Gender: Any gender identity

Ethnicity: Any

Inclusion Criteria:

- 18-49 years old
- Current singleton pregnancy
- GDM diagnosis between 24+0 and 31+6 weeks gestation, and no more than 4weeks from time of diagnosis at time of enrollment.
- Currently receiving gestational diabetes management at the UConn Health Maternal Fetal Clinic, St. Francis Hospital Women’s Health clinic, Hartford Healthcare Women’s Ambulatory Health Services (WAHS)
- Intends to deliver at either UConn Health, St. Francis Hospital or Hartford Healthcare
- Able to read and understand English well enough to participate in the study in English
- Daily access to the internet from smartphone, tablet computer, or laptop/desktop computer that they can use to participate in the study
- Medical clearance to participate from prenatal care provider including clearance to engage in physical activity
- Able to provide verbal or written consent for each component of the study procedures and data collection
- Currently lives within one of the following cities/towns in Connecticut to allow for meal delivery:

Avon	Barkhamsted	Berlin	Bloomfield
Bristol	Burlington	Canton	Cromwell
East Granby	East Hartford	East Windsor	Enfield
Farmington	Glastonbury	Granby	Hartland
Hartford	Manchester	Marlborough	New Britain
Newington	New Hartford	Plainville	Rocky Hill
Simsbury	South Windsor	Southington	Suffield
West Hartford	Wethersfield	Windsor	Windsor Locks

Exclusion Criteria:

- Unable or unwilling to give informed consent or communicate with study staff.
- Diabetes mellitus (Type I or Type II).
- GDM diagnosed prior to 24 weeks gestation or after 32+0 weeks gestation.
- Patient is scheduled for a preterm delivery for medical reasons (i.e., placenta accreta, prior classical incision) at time of eligibility screening or at any time prior to randomization.
- Concurrent participation in another research study providing intervention related to GDM, pregnancy, diet, and/or physical activity.
- Medical conditions that may result in the inability to tolerate solid foods (i.e., hyperemesis gravidarum).
- Medical condition which would prohibit participation as indicated by prenatal care provider providing medical clearance.
- Dietary restrictions that cannot be accommodated for during meal preparation.
- Currently does not live in one of the towns listed within the meal delivery area.

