### **Consent Process**

We request a partial waiver of consent to confirm eligibility screening (via medical chart review or with the referring St. Francis or Hartford Healthcare clinician or clinical staff) for participation in the feasibility study.

Once eligibility has been confirmed and a patient has been confirmed eligible to participate, study staff will conduct an informed consent discussion via phone or virtually using either WebEx or Zoom. A member of the study team will review the consent form with the participant, discuss the research process including why we randomize participants and why follow-up is important, discuss challenges and facilitators of participating in the Meals 4 Moms intervention, and answer any questions the patient has. Following this conversation, staff will email the eligible individual a link to the baseline survey in REDCap. Before proceeding to the survey, participants will review the consent form and provide consent electronically.

As part of the baseline survey, the participant will provide consent for a study team member to contact and obtain medical clearance from a member of the participant's prenatal care team. If medical clearance cannot be obtained within 2 weeks of eligibility screening, the study participant will be considered no longer eligible.

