## Risks

### Risks to Subjects

The possible risks of this study include a food-borne illness, injury while being physically active, episodes of hypoglycemia, possible discomfort from completing questionnaires, and breach of confidentiality. Study activities do not differ from typical everyday activities and risks of pregnant persons with GDM (e.g., eating meals prepared outside of their home such as from restaurants, interacting with others online, using a mobile app) and/or activities done or recommended clinically and in line with national recommendations for diet and exercise during the pregnancy (e.g., eating a ADA compliant diet, regular exercise, measurement of weight) and thus does not pose more than minimal risk/slight increase over minimal risk.

Protection against risks:

Physical Risks:

Meals will be prepared within commercial kitchens by chefs affiliated with My Local Chefs (MLC). The commercial kitchens have been inspected and certified in the prevention of the spread of food borne illnesses by the State of Connecticut Department of Public Health. Participants who receive prepared meals from MLC will be instructed to keep prepared meals refrigerated or freeze to prevent food born illness. Participants will also be provided instructions on how to appropriately reheat the meal for consumption.

Participants must have medical clearance from their prenatal care provider including confirming their ability to engage in physical activity. Medical conditions preventing the increase of physical activity will be exclusionary. We will obtain medical clearance from a member of each participant's prenatal care provider including clearance to participate in physical activity. Research staff will provide additional education about safely engaging in physical activity during pregnancy, and warning signs to watch for. Participants will be encouraged to listen to their bodies during exercise, and to stop exercising if they experience unexpected levels of discomfort or warning signs for physical activity during

pregnancy. Participants who experience discomfort will be asked to meet with their PCP /OBGYN prior to returning to physical activity.

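### Activity clearance is obtained once, before randomisation, and the trainer's two-weekly suggestion to do more has no exception for a participant whose provider has since restricted activity

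*Protocol*

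**What the plan says.** **Before randomisation.** The inclusion criteria in the Protocol (Subject Characteristics) require "Medical clearance to participate from prenatal care provider including clearance to engage in physical activity". Consent Process sets a deadline: "If medical clearance cannot be obtained within 2 weeks of eligibility screening, the study participant will be considered no longer eligible". Data Collection & Randomization lists clearance as a baseline item and halts baseline if it is denied. Randomization adds: "A participant will only be randomized once they have completed all baseline assessments". Risks to Subjects states: "Medical conditions preventing the increase of physical activity will be exclusionary". No section provides for clearance to be renewed, rechecked or withdrawn later.

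**After randomisation, Meals 4 Moms arm.** Under Meals 4 Moms, the trainer first discusses health status and baseline exercise level, sets personal fitness goals and recommends suitable videos. "Participants will then meet with the exercise trainer to review their progress of incorporating exercise into their daily routine on a biweekly basis". Participants also set activity goals in an online planner. Under Activity tracker and digital scale data, the trainer reviews the data every two weeks, compares activity with the 150-minute guideline and will "suggest to the participant to utilize the additional, PI-approved exercise resources within the curated exercise video library to help increase the level of activity". No exception is stated.

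**Safeguards in the same period.** A weekly gain of 1.0 kg or any weekly loss means that "the exercise trainer will inform the study coordinator and/or PI who will contact the participant's prenatal care provider". Risks to Subjects tells participants to stop on unexpected discomfort or warning signs, and adds: "Participants who experience discomfort will be asked to meet with their PCP /OBGYN prior to returning to physical activity". It also has them check glucose before exercise. Serious adverse events, including hospital admission, have their own reporting rules.

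**The concern.** At entry the provider's view on activity is decisive: denial ends the process, and a condition that prevents an increase in activity excludes the patient. After randomisation the same view has no stated effect on what the study encourages. Yet the protocol expects the clinical picture to change. Medical record abstraction lists preeclampsia, fetal growth restriction and hemorrhage among the outcomes to collect. The documents do not say which of these would limit activity, and this point does not assume that any of them would.

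A participant who follows advice to do less will show low activity on the tracker, and low activity is what the trainer's review looks for. Followed as written, the rule then has the study suggest more activity against her provider's advice. What is at stake is the safety of a few participants and the consistency of the advice they receive. No feasibility benchmark depends on it.

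**Working it through.** The plan gives no figure on this point to reproduce. The check has two parts.

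**1. What would catch a restriction given after randomisation?**

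| Provision in the Protocol | What sets it off | Does it stop the trainer's encouragement? |
|---|---|---|
| Stop and see PCP/OBGYN (Risks to Subjects) | Discomfort or warning signs | It acts on the participant; nothing is sent to the trainer |
| Weight rule (Activity tracker and digital scale data) | Gain of 1.0 kg or any loss in a week | The provider is contacted; no step returns activity advice to the trainer |
| Glucose check (Risks to Subjects) | Reading below 70 mg/dl before exercise | No; it leads to a snack |
| Serious adverse event rules (Protections Against Risks to Human Subjects) | Serious events, including admission | They govern reporting and do not cover outpatient advice |
| Fellows at two sites (Screening Procedures; Medical record abstraction) | Eligibility check and outcome abstraction | No stated link to the trainer |
| Biweekly meeting (Meals 4 Moms) | Calendar | It may reveal a restriction; no question about one is required |

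What remains uncovered by rule is a restriction given at an outpatient visit, without symptoms during exercise and without a qualifying weight change.

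**2. Scale**

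Inputs:
- 20 participants in the Meals 4 Moms arm (Sample size and justification).
- 8–11 weeks on average, ending 1 week after delivery (Study Design; Meals 4 Moms).
- One review every 2 weeks (Activity tracker and digital scale data).
- Up to 3 weeks after consent for baseline recalls (Data Collection & Randomization).

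Study Design counts the 8–11 weeks as study participation, which starts at consent. Meals 4 Moms counts them from the first order after randomisation. Both readings are shown.

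- Weeks before delivery, counted from randomisation: 8 − 1 = 7 to 11 − 1 = 10.
- Reviews per participant: 7/2 = 3.5, so 3 complete, to 10/2 = 5.
- Counted from consent with a 3-week baseline: (8 − 1 − 3)/2 = 2 to (11 − 1 − 3)/2 = 3.5, so 3 complete.
- Reviews in the arm: 20 × 3 = 60 to 20 × 5 = 100; from consent, 20 × 2 = 40 to 20 × 3 = 60.
- One affected participant: 1/20 = 5% of the arm.
- Illustration only: a restriction given 4 weeks before delivery leaves 4/2 = 2 reviews at which the suggestion could conflict with it.

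Cost of a pause while a reply is awaited. Assumption: the reply takes 2 weeks, the limit set for initial clearance, so 1 review is lost.

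- Share of that participant's reviews: 1/5 = 20% to 1/3 = 33%; from consent, 1/3 = 33% to 1/2 = 50%.
- Share of the arm's reviews, per affected participant: 1/100 = 1.0% to 1/60 = 1.7%; from consent, 1/60 = 1.7% to 1/40 = 2.5%.

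These figures price the remedy. They do not measure harm: the documents give no complication rate and no list of restricting conditions.

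**The case against.** The strongest reply is that the trainer's role is individual, not mechanical. The trainer knows the participant's health status from the first meeting, sets goals for her and reviews progress with her every two weeks. Asking about progress when activity is low naturally raises the reason. The suggestion is optional, it points to PI-approved material, and the text does not literally say that low activity triggers it; that condition is implied. A provider who restricts activity tells the patient directly, and usual care already includes guidance on exercise. The weight rule is broad, and anyone with discomfort must see a clinician before resuming. Finally, the participant education promised under Risks to Subjects is not reproduced in the protocol and the consent pages are not available here, so a request to report changed advice may exist elsewhere.

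Most of this stands, and it makes the gap narrow. It does not close it. A progress review may bring out a restriction, but the protocol does not require the question, and it states no consequence for the trainer's encouragement if the answer is yes. The statement that no rule exists covers only the text available.

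A reader might go further and infer that participants exercise without safety oversight after entry, or that the study would regularly push them against medical advice. The documents support neither. Several safeguards operate after randomisation, and nothing shows how often a restriction would arise or go unmentioned.

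**Conclusion.** The point holds as a minor gap, best treated as a cheap improvement. Clearance is a single step before randomisation, the rule to suggest more activity carries no exception, and no visible provision requires the trainer to ask about, or act on, an outpatient, symptom-free restriction. The number affected cannot be derived and is probably small; each affected participant is 5% of the arm. The conclusion rests on the visible text and on reading the trainer's suggestion as directed at low activity. The review counts assume that reviews end at delivery. Confidence is medium, because a sensible trainer may well ask anyway. No feasibility outcome or benchmark is put in doubt.

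**What to change.** At each existing biweekly meeting, the trainer asks whether the prenatal provider has changed the participant's activity advice or diagnosed a new pregnancy complication.

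- **Activity restricted:** the trainer pauses all study encouragement to increase activity and informs the coordinator or PI. This covers the suggestion after the tracker review, the personal goals, the recommended videos and the activity goals in the planner. Pausing the suggestion alone would leave the other prompts running.
- **New complication without clear activity advice:** the trainer does not judge its relevance. It goes to the coordinator or PI, who contacts the provider as under the weight rule. Encouragement is paused until the PI finds the complication irrelevant to activity or the provider confirms that she may continue.

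The cost is one question at a meeting already held, an existing referral route and a short amendment. The meeting still takes place, so it still counts towards the protocol's benchmark of at least 80% of trainer sessions completed. The downsides are a pause of up to about one review cycle for the few affected while a reply is awaited, on the two-week assumption, and continued reliance on self-report, now prompted. The SAP is dated 2/12/2026; if pilot follow-up has already ended, the change belongs in the efficacy-trial protocol.

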**Follow up data collection:**

**Post-intervention survey:**

Following the intervention period, participants in both treatment conditions will complete a follow-up survey administered via REDCap. The follow-up surveys will be administered starting at 37 weeks' gestation and up to within 2 weeks following delivery, with a preference to assess 1 week prior to anticipated delivery date. The follow-up survey will include many of the measures asked at baseline, and to rate how acceptable they found their experience with the study. Participants randomized to the M4M condition will also be asked about their satisfaction with meals and acceptability of the intervention. A copy of the follow-up survey is enclosed.

Participants in both treatment conditions will also complete 3 24-hour dietary recalls via the ASA24 online system (2 weekdays and 1 weekend day) using a similar procedure as at baseline.

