### Study Design:

The study has been designed to take place in two distinct phases: Phase 1 – Development of the Meals 4 Moms Program and Phase 2: Feasibility Randomized Control Trial (see enclosed grant proposal). We used feedback from the focus groups conducted in Phase 1 to inform the development of the intervention. **This study protocol covers Phase 2 – the feasibility pilot trial.**

Study participants will be invited to enroll in Phase 2 of the study after being diagnosed with gestational diabetes (up to 4 weeks after diagnosis). Their enrollment in the study will start after consent is obtained and continue until 1 week post-delivery. On average we anticipate study participation to be between 8-11 weeks for most participants. Study participants will be approached during a prenatal care visit to the Women's Health Clinic at UConn Health (UCHC), St. Francis Hospital (SFH), and Hartford Healthcare (HH) after being diagnosed with gestational diabetes mellitus (GDM).

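### The follow-up window has no workable rule for deliveries before 37 weeks, outlasts enrollment by a week and leaves diet-recall timing open, so retention may be understated and diet data may mix pregnancy with postpartum

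*Protocol*

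**What the plan says.** Protocol, Post-intervention survey: "The follow-up surveys will be administered starting at 37 weeks' gestation" and may be done "up to within 2 weeks following delivery, with a preference to assess 1 week prior to anticipated delivery date". The same section places the survey after the program: "Following the intervention period, participants in both treatment conditions will complete a follow-up survey administered via REDCap".

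Protocol, Study Design: "Their enrollment in the study will start after consent is obtained and continue until 1 week post-delivery".

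Protocol, Meals 4 Moms: "Prepared meals will be delivered to the participant's home from their first order post-randomization until 1 week after the" participant gives birth.

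Other statements that bear on the point:

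- **Follow-up diet recalls.** Both arms complete three, by a procedure like the baseline one. The baseline procedure is anchored to consent (within 3 weeks), and no anchor is given for follow-up.
- **Preterm delivery.** Delivery before 37 weeks is an abstracted outcome (Medical record abstraction). The exclusion criteria remove only preterm deliveries already scheduled by randomization.
- **Retention.** In both documents it means completing any part of the follow-up assessment. The benchmark is at least 80% in each arm, and 65% or less marks the main trial as not feasible.
- **Acceptability.** It rests on two likelihood ratings asked in both conditions, with an 80% benchmark. The follow-up survey is where participants rate acceptability.
- **Interview.** It is held in the Meals 4 Moms (M4M) arm only, and the Feasibility Outcomes table places it after delivery.

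The SAP gives no assessment window and does not mention diet quality.

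**The concern.** The survey window is defined by two anchors, gestational age for its opening and delivery for its closing. They work together only when delivery comes at or after 37 weeks. The protocol expects some deliveries before then and does not say what happens to those participants.

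The closing date is also a week later than the stated end of enrollment, and the survey's position relative to the intervention is described in two incompatible ways. The follow-up recalls, the source of the diet data, have no window.

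Two feasibility benchmarks depend on this follow-up. Retention is judged separately in each small arm, and acceptability depends on the survey itself. Diet quality carries no benchmark here, but Aims and Objectives names it among the outcomes intended to be primary in the efficacy trial. The pilot should therefore show what its recalls measure.

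**Working it through.** **Plan's own figures.** 20 + 20 = 40 randomized. With 20 per arm, 80% is 16 retained (four losses allowed) and 65% is 13. One loss is 1/20 = 5 points. The documents state no power or precision target to reproduce.

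**Survey window by date of delivery.** Let d be gestational age at delivery. If 37 weeks must be reached while pregnant, the window never opens for d below 37+0. If 37+0 is read as a calendar date that still arrives after birth:

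- length = max(0, d + 14 days − 37+0)
- part in pregnancy = max(0, d − 37+0)
- part inside stated enrollment = max(0, d + 7 days − 37+0)

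| Delivery | Window, days | In pregnancy | After delivery | Inside enrollment |
|---|---|---|---|---|
| 34+6 | empty (closes 1 day before it opens) | 0 | 0 | 0 |
| 35+0 | closes as it opens | 0 | 0 | 0 |
| 36+0 | 7 | 0 | 7 | 0 |
| 36+6 | 13 | 0 | 13 | 6 |
| 37+0 | 14 | 0 | 14 | 7 |
| 39+0 | 28 | 14 | 14 | 21 |
| 40+0 | 35 | 21 | 14 | 28 |

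**End of participation.** 2 weeks − 1 week = 1 week of permitted follow-up beyond stated enrollment, for every participant.

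**Survey against intervention.** The preferred time is 7 days before anticipated delivery, and meals run to 7 days after delivery. If delivery falls on the anticipated date, the preferred survey comes 7 + 7 = 14 days before meals end.

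**Recalls.** If they followed the survey window (an assumption), a 39+0 delivery in the M4M arm would allow 14 days in pregnancy, 7 postpartum on meals and 7 postpartum after meals end. These are available calendar days and do not predict where recalls will fall.

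**Retention, upper bound.** The documents give no preterm rate, so I assume p = 5% to 20% among those randomized. I also assume that every preterm delivery is lost to follow-up and that other retention is r = 90%, independent of preterm delivery and of arm. Effective retention is r(1 − p). The chance of at least 16 of 20 is an exact binomial tail.

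| p | Expected preterm per arm (20p) | r(1 − p) | One arm reaches 16/20 | Both arms do |
|---|---|---|---|---|
| none lost | – | 0.900 | 0.96 | 0.92 |
| 5% | 1 | 0.855 | 0.85 | 0.72 |
| 10% | 2 | 0.810 | 0.67 | 0.45 |
| 15% | 3 | 0.765 | 0.48 | 0.23 |
| 20% | 4 | 0.720 | 0.30 | 0.09 |

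The chance of five or more preterm deliveries in an arm, which on this assumption would alone put it below 16/20, runs from 0.003 (p = 5%) to 0.37 (p = 20%).

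**Who can still count as retained.** The 37-week start is attached to the survey. Neither the recalls nor the interview carries it. Subject Compensation ties the M4M follow-up payment to both survey and interview, which supports counting the interview as follow-up. An M4M participant who delivers preterm thus has two other routes to being retained, and a usual-care participant has one.

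**The case against.** The strongest reply is that staff would use common sense. The closing phrase can be read as covering every delivery, and on the calendar reading deliveries after 35+0 and up to 36+6 keep up to 13 days. That is fair. The effect depends on the reading, and it is a gap in the rule, not proof that anyone will be missed.

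A reader might go further and infer that the window turns preterm participants into losses, so that 1 to 3 of the four allowed losses are used up at a 5% to 15% preterm rate. The documents do not support that. Retention counts any part of follow-up, so a recall or an interview is enough. The preterm rate is assumed, and deliveries already scheduled preterm are excluded. The retention table above is a worst case.

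A reader might also infer that diet quality is mismeasured. The documents do not say that recalls will fall in the survey window or be averaged across pregnancy and postpartum. What they show is that recall timing is unspecified and mixing is possible. Diet quality is only described in this trial.

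What survives is the one-week conflict, the missing rule for preterm delivery, the contradictory position of the survey and the unspecified recall window. The any-part definition of retention also leaves two problems. It does not rescue the acceptability ratings, which need the survey, and its extra route, the interview, exists in one arm only.

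**Conclusion.** The concern holds as a gap and an inconsistency in the timing rules, with consequences that are possible but not shown. The one-week overrun and the conflict over whether the survey follows the intervention need no assumption. The survey window is unusable for all deliveries before 37+0 on the literal reading. On the calendar reading it is empty before 35+0 and shorter than two weeks up to 36+6.

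Acceptability ratings may therefore be missing for preterm deliverers. Retention may be understated, more so in usual care, by 5 points per participant lost in an arm of 20. How many are lost depends on a preterm rate the documents do not give and on how staff apply the window. Recalls may mix pregnancy, postpartum on meals and postpartum after meals. No benchmark rests on that, but unlabelled mixing weakens what the pilot can tell the efficacy trial. The point is worth correcting and does not undermine the trial.

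**What to change.** (a) Open the follow-up window at 37+0 or at delivery, whichever comes first, in both arms.

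(b) Reconcile Study Design, Meals 4 Moms and Post-intervention survey on when participation ends and where follow-up sits relative to the intervention. The meal schedule need not change for this.

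(c) Give the follow-up recalls a stated window with the same preference for assessment before delivery. Record each recall's date relative to delivery and to the end of meals. Have the SAP describe diet quality by that timing and by arm, keeping all recalls and showing the number of preterm deliveries. A summary of pre-delivery recalls alone should not be the sole main measure. Even with (a), anyone delivering by 37+0 has no pre-delivery recall unless the recall window opens earlier, so that summary would drop preterm deliverers on an event occurring after randomization.

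The SAP is dated 2/12/2026, so collection may already be complete. In that case (a) is no longer possible, but (c) can still be done where dates were recorded. Retention and acceptability can then be reported by arm with preterm deliveries identified.

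The cost is some wording in both documents and a timing variable. The downside is small subgroups in the timing tables.
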